### **Objectives**

This project focuses on the deleterious effects of fructose-containing beverages on lipid metabolism. Our hypothesis is that consumption of fructose-containing beverages increases *de novo* lipogenesis (DNL) with numerous consequences on lipid and glucose metabolism, insulin resistance, inflammation and blood pressure. We further propose that fructose also decreases the removal of triglyceride-rich lipoproteins (TRLs) from the circulation by inhibiting the activity of lipoprotein lipase (LPL), a key enzyme in lipoprotein metabolism. We therefore focus our study on the effects of fructose on postprandial lipemia and features of ectopic fat deposition including visceral adipose tissue and liver fat content which are key features of individuals with metabolic syndrome and type 2 diabetes. So far, little data exist on the pathophysiological responses to fructose-containing beverages in obese subjects with multiple cardiometabolic risk factors. We will test the hypothesis that hypertriglyceridemic (HTG) obese subjects are particularly prone to the deleterious effects of fructose-containing beverages compared to normolipidemic (NTG) obese subjects. We have therefore designed our study to differentiate the weight-dependent vs. weight-independent effects of fructose-rich diet in HTG and NTG obese subjects.

### **Background**

Obesity has become a contemporary global health hazard affecting not only adults but also adolescents and children. The prevalence of obesity in children as well as in adults is rising rapidly both in USA and Europe. In parallel with obesity, the prevalence of type 2 diabetes and cardiovascular disease (CVD) is increasing dramatically and this portends a new wave of CVD. In the face of this major health problem a better understanding of factors contributing to a positive energy balance and to body fat gain is necessary, particularly regarding factors related to the development of visceral obesity associated with excess ectopic and liver fat, which is the most dangerous form of obesity.

Notably, consumption of sugar-sweetened beverages (SSB) has increased steadily over the past decades and is identified as the major source of added sugar intake accounting for a major part of excess energy intake. A major dietary change over the past decades has in fact been the dramatic increase of fructose intake due to increased consumption of soft drinks and juice beverages. The fructose intake has increased by about 20 % per capita in USA between 1970 and 2005 and the present daily intake (approximately 55 g) accounts for about 10 % of the total daily caloric intake. Recently, large epidemiological studies have documented the association between SSB consumption and increased risk for obesity, type 2 diabetes and CVD. Furthermore, recent meta-analyses reported that the risk to develop type 2 diabetes was increased by 26 % in the highest quintile of SSB intake which corresponds to the consumption of 1-2 soft drinks per day.

Strong evidence indicates that added fructose, a component of sucrose and high fructose corn syrup, has specific deleterious cardiometabolic effects as compared to glucose. A high fructose diet is linked with dyslipidemia, insulin resistance/glucose intolerance, visceral obesity and inflammation independently of body weight changes. In addition, fructose has been reported to raise blood pressure when consumed as SSBs whereas glucose does not appear to have such deleterious effect. Thus, all sugars are not equal in respect to their adverse metabolic effects. Of note, fructose derived from fruits and high-fiber cereal products are considered beneficial. It is critically important to recognize the SSBs as the major source of not only extra calories but also of excess fructose. Excessive intake of SSB has turned out to be a serious public health problem and a restriction of SSBs should be a major target in the prevention against obesity, type 2 diabetes and CVD. To succeed in this fight it is critical to better understand the mechanisms by which excess fructose consumption contributes to the health hazards of obesity, particularly in the etiology of the related atherogenic dyslipidemia.

## Dietary sugar intake and cardiometabolic health at the population level

Recently, the association of blood lipid levels and consumption of added sugars was studied in the adult population in the National Health and Nutrition Examination Survey (NHANES) ( $n= 6113$ ). In this American cross-sectional study higher fructose consumers had more unfavorable lipid levels, namely significantly lower HDL cholesterol, higher triglycerides and a high ratio of triglycerides to high density lipoproteins (HDL) whereas women also had higher low density lipoprotein (LDL) cholesterol levels. Likewise, in the Framingham study daily soft drink consumers had higher incidence of elevated triglycerides and low HDL cholesterol than non-consumers (relative risk: 1.22 and 1.22, respectively).

Several studies have consistently reported increased responses of fasting and postprandial triglyceride levels and 24 hr profiles to short term feeding of fructose as compared to glucose in both lean and obese subjects. These perturbations directly lead to other lipid abnormalities including elevation of apo-B levels, accumulation of small dense LDL, and increased remnant lipoproteins, combined with reduced HDL cholesterol which all are components of the atherogenic lipid triad, a strong risk factor for CVD. Interestingly, the deleterious effect of fructose on lipid metabolism is directly linked to the daily intake; a fructose intake  $> 50$  g/ day is associated with postprandial hyperlipidemia whereas intake above 100 g/day also results in elevation of fasting serum triglycerides. **Thus, fructose intake is directly linked to an atherogenic dyslipidemia.**

## Metabolic consequences of fructose feeding

Fructose is rapidly taken up by the hepatocytes from the portal circulation and found only in micromolar concentrations in the systemic circulation. Therefore, high fructose intake primarily alters hepatic glucose and lipid handling. The low glycemic index of fructose has been considered beneficial especially for diabetic subjects, but recent evidence suggest that the harms of added fructose outweigh its glycemic benefits. Although fructose does not stimulate acute insulin excursion like glucose, fructose has adverse effects on glucose metabolism and insulin sensitivity. In addition, fructose seems to trigger deleterious endocrine signals that are reflected in energy metabolism.

Furthermore, fructose (in contrast to glucose) does not stimulate ghrelin secretion which together with low postprandial insulin response contributes to lower satiety and possibly overeating after fructose vs. glucose. Fructose is also associated with a blunted leptin response. **In summary, fructose intake is linked with an endocrine profile potentially favoring extra energy intake and weight gain.**

## POTENTIAL MECHANISMS UNDERLYING FRUCTOSE INDUCED HYPERTRIGLYCERIDEMIA

### Regulation of very density lipoprotein (VLDL) metabolism

Serum triglyceride concentration reflects the balance between the secretion and removal of triglyceride-rich particles (TRLs). We have recently reported that overproduction of large VLDL1 particles is the hallmark of dyslipidemia in the metabolic syndrome and type 2 diabetes. We also reported that liver fat is one driving force that aggravates overproduction of VLDL particles in insulin resistance. Our results also provided the first *in vivo* evidence that insulin down regulates VLDL1 secretion in subjects with low liver fat while the suppression of VLDL1 secretion by insulin is hampered in subjects with high liver fat.

[figure not shown]
We recently reported that hypertriglyceridemia in abdominally obese subjects is due to dual metabolic defect, namely the combination of increased secretion and severely impaired clearance of triglyceride-rich VLDL1 particles. Increased liver and subcutaneous abdominal fat were linked to overproduction of VLDL1 particles whereas increased plasma levels of apo-CIII associated with impaired catabolic rate of VLDL1 particles in obese HTG compared to NTG subjects. The disturbed hepatic lipid metabolism is also critical in the pathogenesis of hepatic steatosis, and it has been suggested that the inability of the liver to secrete triglyceride-rich VLDL particles causes hepatic steatosis. This concept considers VLDL-secretion as a way to protect liver against excess lipid accumulation and lipotoxicity.

In clinical practice, it has been suggested that the presence of an elevated waist circumference together with increased fasting triglyceride concentrations, the so-called *hypertriglyceridemic waist phenotype*, could represent a useful and simple screening approach to identify individuals likely to be characterized by excess ectopic fat deposition and the related dysmetabolic profile.

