**Experimental diets**

Subject eligible for the study **will be randomly assigned to one of the two diet groups for 12 weeks:**

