### **Power calculations**

Primary endpoints in the current study are 1) change in plasma triglyceride (TG) area under curve (AUC) between the NTG and HTG during fructose feeding (between groups) and 2) change in TG AUC in HTG subjects during isocaloric fructose vs. hypercaloric fructose feeding (within group). The calculations are based on following assumptions: TG AUC increases from 7 to 10.5 mmol/l×hrs in normotriglyceridemic and from 7-9 to 14 mmol/l×hrs in hypertriglyceridemic subjects during fructose. Standard deviation is assumed to be 4.3 based on previous studies in similar groups of patients. 1) To detect significant difference (>3.5 mol/l×hrs) between the groups ( $n=25$ ) with unpaired t-test. 2) To detect significant increase (>3.5 mol/l×hrs) within the group ( $n=15$ ) with paired t-test. These calculations assume that alpha = 0.05 and power = 0.80 in all tests.

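### Primary endpoint 1 compares HTG with NTG men, a contrast that is not randomised, and the only test named for it is an unpaired t-test that ignores diet arm and any imbalance in adiposity or age

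*Protocol*

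**What the plan says.** Under Experimental diets, eligible men are "randomly assigned to one of the two diet groups for 12 weeks". Diet is therefore the only randomised factor. HTG or NTG status is a trait the men bring with them.

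Power calculations defines primary endpoint 1 as "change in plasma triglyceride (TG) area under curve (AUC) between the NTG and HTG during fructose feeding (between groups"). The test is named in the same section: the difference is to be detected "between the groups ( $n=25$ ) with unpaired t-test". The protocol states no covariate, matching or stratification for this contrast.

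The hypothesis behind it, in Objectives, is that "hypertriglyceridemic (HTG) obese subjects are particularly prone to the deleterious effects of fructose-containing beverages compared to normolipidemic (NTG) obese subjects".

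The section on regulation of VLDL metabolism describes earlier work in obese HTG and NTG subjects: "Increased liver and subcutaneous abdominal fat were linked to overproduction of" VLDL1 particles. It adds that a large waist with raised triglycerides serves as a simple screen for people likely to carry excess ectopic fat.

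**The concern.** Randomising diet balances the two diet arms. It does nothing to balance HTG against NTG men. If the phenotypes differ at baseline in BMI, waist or age, and these also affect how much TG AUC rises on fructose, an unpaired t-test credits that part of the difference to phenotype. The protocol's own background makes a difference in fat depots plausible. The entry limits (BMI 27 to 40 kg/m², age 20 to 65 years) leave room for differences in BMI and age.

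The same t-test also leaves out the randomised diet arm. One diet is designed to allow weight gain and the other to keep weight stable, so arm is an obvious source of variation in the outcome.

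What is at stake is how the leading endpoint is read. A positive result could be taken to mean that raised triglycerides make obese men more sensitive to fructose, when part of it reflects greater adiposity or a different age. A larger sample does not remove such a bias. It makes the test more likely to declare it significant.

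**Working it through.** **Inputs from the protocol (Power calculations; Study design).** Target difference 3.5 mmol/l×hrs (printed there as mol/l×hrs); SD 4.3; alpha 0.05; power 0.80; 25 men, read as per group; 128 men in total.

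**Inputs assumed, because the documents give none.**
- Standardised baseline imbalance s between HTG and NTG in one factor: 0.3 to 0.8 SD.
- Correlation r of that factor with the change in TG AUC: 0.2 to 0.4.
- SD 4.3 applies to the change in TG AUC, and tests are two-sided.
- For the larger sample only: all 128 men split 64/64 by phenotype.

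**Step 1: the plan's own figure.** With effect size 3.5 / 4.3 = 0.814, the exact two-sided t-test needs 24.69, so 25 per group, with power 0.805 at 25. The stated 25 reproduces. The sizing therefore rests on the plain t-test, and there is no arithmetic error in it.

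**Step 2: bias in the raw difference.** Bias = s × r × 4.3.
- Low end: 0.3 × 0.2 × 4.3 = 0.26.
- Middle: 0.5 × 0.3 × 4.3 = 0.64 (0.645 / 3.5 = 18% of the target).
- High end: 0.8 × 0.4 × 4.3 = 1.38 (1.376 / 3.5 = 39% of the target).

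**Step 3: how often the t-test rejects with no phenotype effect.** The standard error is 4.3 × √(2/n), which is 1.216 at 25 per group and 0.760 at 64 per group. The two-sided noncentral t at alpha 0.05 gives:

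| s | r | Bias (mmol/l×hrs) | Rejection, 25 per group | Rejection, 64 per group |
|---|---|---|---|---|
| 0.3 | 0.2 | 0.26 | 5.5% | 6.3% |
| 0.5 | 0.3 | 0.64 | 8.1% | 13.4% |
| 0.8 | 0.4 | 1.38 | 19.8% | 43.5% |

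Here no phenotype effect means no effect of triglyceride status beyond the imbalanced factor.

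**Step 4: price of adjusting for one such factor.** The required n per group is about 24.69 × (1 + s²/4) × (1 − r²). The first factor is the loss from the overlap of phenotype and covariate; the second is the gain from explained variance.
- Dearest corner, s = 0.8 and r = 0.2: 24.69 × 1.16 × 0.96 = 27.5, so 28.
- Cheapest corner, s = 0.3 and r = 0.4: 24.69 × 1.0225 × 0.84 = 21.2, so 22.

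With a wider assumed range (s 0.5 to 1.0, r 0.3 to 0.5) the result is 20 to 29. All are well within 128 men.

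**The case against.** **The question is about phenotype.** Objectives asks whether HTG obese men are more prone to harm, not whether the triglyceride level itself is the cause. The background treats excess ectopic fat as part of the hypertriglyceridemic picture. On that reading, a difference that travels with liver fat is a real phenotype difference, and calling it a false positive would be wrong. This stands. It is why the raw difference remains a valid description and why liver fat does not belong in the main adjusted model. It does not cover age or general obesity, and the protocol sets out to compare HTG with NTG among obese men.

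**The t-test appears only under the sample size.** A statistical analysis plan, not shown here, may specify another model. This stands in part: a reader might infer that the final analysis is fixed as unadjusted, and the protocol does not establish that. But the same section defines the primary endpoint and is the only place where a test is attached to it.

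**The figures are assumed.** They are. The imbalance, the correlation and the 64/64 split have no source in the protocol, and the 44% needs both extremes and the larger sample together. The entry criteria also narrow the field (men only, non-smokers, stable weight, no diabetes), and analysing change cancels stable differences in TG AUC level. It does not cancel differences in response that go with adiposity or age.

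**Two stronger readings are not supported.** A reader might infer that the protocol says HTG men habitually consume more fructose. It does not. The section on dietary sugar and cardiometabolic health reports that in a general adult survey "higher fructose consumers had more unfavorable lipid levels, namely significantly lower HDL cholesterol, higher triglycerides"; that runs from intake to lipids and is not about these two groups. A reader might also infer that the central conclusion would have no support in either direction. That goes too far: the raw contrast still shows an association, and the middle assumptions give a bias of 18% of the target.

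**Conclusion.** The point holds in a limited form. Primary endpoint 1 is a non-randomised comparison, and the only method the protocol names for it ignores diet arm and any imbalance in BMI, waist or age. The result can say which phenotype responds more. It cannot show that triglyceride status matters beyond adiposity or age.

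The true size of the bias cannot be derived from the documents. Under the assumed ranges it is 0.26 to 1.38 mmol/l×hrs, and the rejection rate without a phenotype effect is about 5.5% to 20% at the planned 25 per group (6% to 44% at 64 per group). These are illustrations of scale, not estimates for this trial. The point is worth acting on because a better method is available from data already collected.

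**What to change.** 1. State in the protocol that endpoint 1 is a non-randomised comparison of phenotypes, and word its conclusion as an association.
2. Replace the unpaired t-test with a linear model of change in TG AUC on phenotype and randomised diet arm, adjusted for baseline BMI (or waist) and age.
3. Report the unadjusted difference beside it as the descriptive result.
4. Prespecify secondary models that add habitual fructose intake from the baseline 3-day diet record, and baseline liver and visceral fat from the imaging visit. Keep these secondary, because liver fat may be part of the HTG phenotype and adjusting for it changes the question.

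The cost is a few lines of text, extraction of fructose intake from the baseline record, and a few degrees of freedom. BMI, waist and ectopic fat are already measured, and age is known from eligibility. No added covariate makes the phenotype contrast causal, so the label in item 1 is needed whichever model is used.

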### Regulation of *de novo* lipogenesis (DNL) in the liver

The liver X receptor (LXR) and the farnesoid receptor (FXR) play critical roles in the regulation of DNL and triglyceride synthesis via the transcription factors sterol response element-binding protein 1c (SREBP-1c) and carbohydrate response element-binding protein (ChREBP) that are major regulators of DNL via activation of fatty acid synthase (FAS) and stearoyl-CoA desaturase (SCD). The SREBP-1 is a master regulator of hepatic lipogenesis (Figure 1). The peroxisome proliferator-activator receptor gamma

coactivator-1 $\beta$  (PGC-1 $\beta$ ) coactivates SREBP-1c. ChREBP is also considered to be a hepatic carbohydrate sensor and it is activated by both glucose and fructose. An intriguing observation is that SREBP1-c seems also to be activated by fructose independently of insulin. Knockdown of PGC-1 $\beta$  resulted in reduced expression of SREBP-1, and downstream lipogenic genes in the liver prevent both fructose-induced hypertriglyceridemia and hepatic insulin resistance. Collectively these actions mediate the lipogenic effects of fructose in the liver by enhancing its lipogenic potential and deposition of fat in the liver. Notably, DNL has been reported to be enhanced in subjects with NAFLD.

**Fig 1. Mechanisms for fructose-induced hepatic de novo lipogenesis**

The final step in triacylglycerol synthesis is regulated by diacylglycerol transferase-2 (DGAT2) that transfers FA from fatty acyl CoA to diacylglycerol (DAG). Knockdown of DGAT2 expression *in vivo* associates with reduction of liver fat. The accumulation of DAG in liver triggers the activation of protein kinase C (PKC) serine-threonine kinase. PKC is highly expressed in the liver with subsequent impairment of insulin signaling and is a link between insulin resistance and fatty liver. An intriguing observation is that DAGs comprised of unsaturated acyl chains are more potent activators of PKC than those containing saturated acylCoAs. Stearyl-CoA desaturase (SCD)-1 is a key enzyme converting saturated FAs to monosaturated FAs and

it is reported to be a good surrogate marker for DNL. Recently hepatic DAG concentration measured from liver biopsies was reported to correlate with liver fat percent.

In addition to glycerolipids another candidate to interfere with insulin signaling in the liver is the accumulation of ceramides molecules of sphingolipids family. Ceramides not only interfere with insulin signaling but also interact with inflammation and stress signaling and mitochondrial function. Both increases of DAGs and ceramides are enhanced upon fatty acid oversupply and reflect a shift of fatty acyl CoAs between different metabolic pathways. To elucidate the role and impact of these lipids on metabolism request new technology utilizing specific platforms of ultra-performance liquid chromatography (UPLC)/mass spectrometry (MS) based lipidomic analyses. In this protocol we will track the responses of major lipid components in TRL fraction to the dietary changes. **In summary, the data support strongly the concept that the effects of glucose and fructose on lipid metabolism are not equal with respect to lipid metabolism and that hepatic insulin resistance covers not only glucose pathway but also pathways of lipid metabolism.**

### Apo-CIII and VLDL assembly

Apo-CIII is an apolipoprotein carried not only in TRLs and HDL particles but also in LDL in circulation. Several studies have shown that apo-CIII is a determinant of serum and VLDL triglycerides (TG) as well as of VLDL catabolic rate since it functions as an inhibitor of lipoprotein lipase (LPL), the rate limiting enzyme of TG lipolysis. Interestingly, VLDL apo-CIII production rate correlates closely with that of VLDL-TG in centrally obese men. Notably, the apo-CIII activity is influenced the dietary composition, and unsaturated fats have been shown to decrease apo-CIII as well as serum triglycerides. Recent data suggest that apo-CIII is not only linked to the turnover of TRLs but may also be linked to the biosynthesis of VLDL particles. The observation that VLDL-apoCIII production is stimulated by plasma free fatty acids in humans implicate that apo-CIII may enhance the production of large VLDL particles in the setting of excess TG availability as seen in NAFLD. This mechanism may also explain why carriers of specific apo-CIII variants (C-482TM and T-455C) have elevated serum triglycerides and apo-CIII that associated with an increased prevalence of non-alcoholic fatty liver disease (NAFLD). Intriguingly, a novel mechanism has recently been indentified that links glucose and plasma TG metabolism via the regulation of apo-CIII expression by glucose (Caron S *et al.* submitted). This mechanism involves the transcription factors ChREBP and hepatocyte nuclear factor receptor  $\alpha$  (HNF-4 $\alpha$ ). As ChREBP is activated by both glucose and fructose this is a novel mechanism explaining how fructose may enhance lipogenesis in the liver. **In summary, emerging results clarify how glucose influences apo-CIII expression, but no data exists on the response of apo-CIII to fructose intake.**

## Genes influencing TRL metabolism

Common genetic variations predisposing to dyslipidemia among subjects with and without type 2 diabetes include genes regulating lipid metabolism in the liver and VLDL clearance from circulation. Overall genetic variants seem to account for one-third of the susceptibility to high TG. Recently, allelic variants of the MLX interacting protein-like (MLXIPL) gene were reported to associate with high triglyceride levels. Interestingly, this gene controls hepatic energy metabolism, specifically lipogenesis from sugars through ChREBP. Other genes regulating different steps in VLDL synthesis include microsomal triglyceride transfer protein (MTP), APO-B, glucokinase hexokinase 4 regulatory protein (GCKR), polypeptide N-acetylgalactosaminyltransferase 2 (GALNT2) and DGAT2. Recent studies have found that common variants in the APO-CIII gene and palatin-like phospholipase domain containing 5 (PNPLA5) contributed to fatty liver. APO-CIII and APO-A5 are a part of gene cluster on chromosome 11. Both APO-CIII, APO-A5 and angiopoietin-like 3 (ANGPTL3) genes are important regulators of serum TG level by LPL mediated clearance of TRLs. Other genes regulating clearance capacity include LIPG (endothelial lipase), hepatic lipase (HL) and glycosylphosphatidylinositol (GPI)-anchored HDL-binding protein 1 (GPIHBP1). If fructose consumption results to more pronounced DNL, to storage of TAG in the liver and postprandial lipemia in carriers of these common variants has not been studied.

[figure not shown]
This study aims to examine the diet-gene interactions by comparing the differences in dietary responses of postprandial lipemia between carriers and non-carriers of common variants of approximately 40 genes shown to associate with triglyceride metabolism (in particular variants in MLXIPL, GCKR, GALNT2, APOB, APOA5, LIPG, HL, LPL and ANGPTL3 as well as combined effects of many risk variants in all 40 genes). We will further study expression quantitative trait loci (eQTLs) comparing mRNA transcript levels and their changes in response to glucose load in adipose tissue biopsies in hyper- vs. hyporesponders to fructose.

Hepatic heparan-sulfate proteoglycans (HSPGs) are important to mediate TRL clearance by the liver, and recent studies have shown that changes in the composition of hepatic HSPGs resulted in profoundly reduced clearance of TLRs. HSPG synthesis is regulated by >35 genes, of which syndecan-1 and genes associated with initiation (exostosin: EXT1/2) or sulfation (N-deacetylase sulfotransferase: NDST1 as well as 2-O-sulfotransferase: HS2ST1) of HSPG have all been associated with TRL uptake in vitro. Degradation of HSPG is regulated by 2 enzymes; heparanase (HPSE) and sulfatase (SULF). In humans, little is known on the 'metabolism' of HSPGs in health or disease, whereas data on the effect of changes in HSPG metabolism on cardio-metabolic homeostasis is entirely unknown. We will therefore study the impact of genetic variations in HSPG-related genes and triglyceride metabolism.

